**11.6.4. Safety**

Extent of Exposure
Treatment Exposure During the Run-in and Stabilization Periods

 
• Duration of exposure to FSC during the run-in period is calculated as:             
 
• Run-in treatment stop date – Run-in treatment start date +1
 
 
 
• Duration of exposure to FF/VI 100/25 during the stabilization period is calculated as:             
 
• Stabilization treatment stop date – Stabilization treatment start date +1
 
 
 
• Exposure during the run-in and stabilization phase will be summarized as continuous and using the following categories:             
 
○ <math>\geq 1</math> day, <math>\geq 1</math> weeks, <math>\geq 2</math> weeks, <math>\geq 3</math> weeks (Run-in period only)
 
 
 
 
In case of missing dates, no imputation will be performed. Exposure will be considered missing.

Randomized Treatment Exposure and Post-Treatment On-Study Duration

 
• Duration of treatment exposure to study treatment is calculated as:             
 
• treatment stop date – treatment start date +1
 
 
 
• Duration of Post-treatment time spent on study is calculated as:             
 
○ Last Scheduled Clinic Visit (i.e., Visit 8 (EOS Visit) or Early Withdrawal Visit) – (treatment stop date+1).
 
 
 

Randomized Treatment Exposure Categories

 
• Treatment Exposure will be summarized as continuous, and using the following categories:             
 
○ <math>\geq 1</math> day, <math>\geq 4</math> weeks, <math>\geq 8</math> weeks, <math>\geq 12</math> weeks, <math>\geq 16</math> weeks, <math>\geq 20</math> weeks, <math>\geq 24</math> weeks, <math>\geq 28</math> weeks, <math>\geq 32</math> weeks, <math>\geq 36</math> weeks, <math>\geq 40</math> weeks, <math>\geq 44</math> weeks, <math>\geq 48</math> weeks and <math>\geq 52</math> week, 24 weeks (-5/+2 days), 36 weeks (-5/+2 days), 52 weeks (-5/+2 days)
 
○ 24 weeks (-5/+2 days) will be based on Day 169. 36 weeks (-5/+2 days) will be based on Day 253. 52 weeks (-5/+2 days) will be based on Day 365.                 
 
○ Subjects whose planned End of Study visit is Week 36 or 52, are included if their Week 24 visit falls within the protocol permitted visit window and they are still on study treatment at this visit.
 
○ Subjects whose planned End of Study visit is Week 52, are included if their Week 36 visit falls within the protocol permitted visit window and they are still on study treatment at this visit.
 
 
 
 
 

Post-treatment On-Study Duration

 
• Post-treatment On-Study duration will be summarized as continuous and using the following categories:             
 
○ Duration (Week): (0, 4], (4, 12], (12, 24], (24, 36], > 36
 
 
 

Adverse Events	
Adverse Event Rate	

 
Event rate per thousand person-years will be displayed on most On-Treatment AE data displays listed in Section 11.10.8. Event rate per thousand person-years will be calculated as the number of events x 1000 divided by the total participant exposure during the time-period of interest.
 
	
On-treatment adverse events by time in study	

The following data/participants with data will be included in the AE summaries for specific time periods. Exposure for the time periods will also be calculated as defined below to allow the presentation of rates.
	
Time point	Data to be included
Up to 24 weeks	
 
If participants planned EOS visit is week 24: up to last treatment date +1
 
If participants planned EOS visit is later than week 24 use data up to the minimum (169, last treatment date+1)
 

Up to 36 weeks	
 
If participants planned EOS visit is week 24: exclude from summary table
 
If participants planned EOS visit is week 36: up to last treatment date +1
 
If participants planned EOS visit is week 52 use data up to the minimum (253, last treatment date+1)
 

Up to 52 weeks	
 
If participants planned EOS visit is week 24: exclude from summary table
 
If participants planned EOS visit is week 36: exclude from summary table
 
If participants planned EOS visit is week 52 use data up to last treatment date+1
 

Maximum/Minimum Post-Baseline and Worst-Case Post-Baseline	
Definition	Reporting Details
Maximum post-baseline	Maximum value over all on-treatment timepoints
Minimum post-baseline (Assessments that do not have a lower limit = 0)	Minimum value over all on-treatment timepoints
Worst case post-baseline (ECG findings)	
 
'Abnormal' if any on-treatment assessment is evaluated as 'Abnormal'
 
'Unable to evaluate' if all on-treatment assessments are 'Unable to evaluate'
 
'Normal' if any on-treatment assessment is evaluated as 'Normal' and there are no on-treatment assessments evaluated as 'Abnormal'
 

**Note:** Assessment of minimum/maximum/worst-case post-baseline will include on-treatment data from scheduled, unscheduled and study discontinuation visits (if applicable).

Laboratory Parameters

 
• Non-quantifiable laboratory results will be treated as missing in summary displays. However, the results will be listed as received (e.g. '<x' or '>x').
 
• An 'any visit post-baseline' classification will be derived, in which participants will be counted in the 'low' and 'high' categories if they reported a low or high value at any scheduled or unscheduled on-treatment visit during the study.
 
• Change from baseline values will be classified relative to the normal range as 'to low', 'to normal or no change' or 'to high'. Participants who do not change categories or move from out-of-range to normal will be classified as 'to normal or no change'.
 
• An 'any visit post-baseline' change classification will be derived, in which participants will be counted in the 'to low' and 'to high' categories if they reported a change from a 'normal' baseline to a value below or above the normal range (respectively) at any on-treatment scheduled or unscheduled visit during the study. Participants who did not report a change to a value outside the normal range at any visit after the start of study treatment will be counted in the 'to normal or no change' category.
 

Multiple Measurements for Post-Baseline Visits for Safety

 
• Participants having both high and low values relative to normal ranges at post-baseline on-treatment visits for safety parameters will be counted in both the high and low categories of the "any visit post-baseline" row of related summary tables.
 

Urinalysis

Potential Clinical Importance is defined as an increase in Protein or Occult Blood post-baseline relative to Baseline (Screening), or if microscopy is performed.

ECG			
QTcF and QTcF change from baseline results will be reported in categories as below			
ECG Parameter	Units	Ranges	
		Lower	Upper
Absolute			
Absolute QTcF Interval	msec	0	≤ 450
		> 450	≤ 480
		> 480	≤ 500
		> 500	≤ 530
		> 530	
Change from Baseline			
Change from Baseline QTcF	msec		≤ -60
		> -60	≤ -30
		> -30	≤ 0
		> 0	≤ 30
		> 30	≤ 60
		> 60	

Pneumonia (AESI)
Pneumonia Event Rate

 
• Pneumonia events will be events classified in the pneumonia AESI group (rather than events recorded on the Pneumonia Details eCRF page).
 
• Pneumonia event rate will be calculated as the number of events x 1000 divided by the total participant exposure during the time period of interest.
 

Association of Chest X-Ray with Pneumonia Event

 
• A chest X-ray is considered associated with pneumonia if it is performed within -7 to +14 days of the date of onset of pneumonia. Pneumonia is considered to be supported by a chest X-ray if the finding of the associated X-ray is consistent with the diagnosis of pneumonia, as recorded on eCRF page for chest X-ray.
 

MACE	
Broad MACE criteria	Narrow MACE criteria
Ischaemic heart disease SMQ: 
 
• Myocardial infarction SMQ (excluding fatalities)
 
• Other ischemic heart disease SMQ (excluding fatalities)
 
 Central nervous system haemorrhages and cerebrovascular conditions SMQ (excluding fatalities)	-Myocardial infarction PT (excluding fatalities) -Acute myocardial infarction PT (excluding fatalities)  Central nervous system haemorrhages and cerebrovascular conditions SMQ (excluding fatalities)

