## 8.5. Clinical Laboratory Analyses

On-treatment laboratory evaluations including the analyses of Chemistry laboratory tests, Hematology laboratory tests, Urinalysis, and liver function tests will be based on GSK Core Data Standards. The details of the planned displays are in [Appendix 10: List of Data Displays](#)

Laboratory values will be classified as 'Low', 'Normal', or 'High' based on the provided normal ranges.

Change from baseline values will be classified relative to the normal range as 'To Low', 'To Normal or No Change', or 'To High'. Participants who do not change categories or move from out-of-range to normal will be classified as 'To Normal or No Change'.

An 'any time post-baseline' change classification will be derived for each treatment in which participants will be counted in the 'To Low' or 'To High' categories if they reported a change from a 'Normal' baseline to a value below or above the normal range, respectively, at any on-treatment scheduled, unscheduled, or EW visit during the associated treatment. Participants who did not report a change to a value outside the normal range at any visit while taking the associated treatment will be counted in the 'To Normal or No Change' category.

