3.64.	ITT	SAFE_T7	Summary of On-Treatment Major Adverse Cardiac Events (MACE) per Thousand Person-Years – Narrow Definition		SAC
3.65.	ITT	SAFE_T7	Summary of On-Treatment Major Adverse Cardiac Events (MACE) per Thousand Person-Years – Broad Definition		SAC

Safety: Tables					
No.	Population	IDSL ID / Example Shell	Title	Programming Notes	Deliverable [Priority]
Pneumonia and Radiography (Chest X-Rays)					
3.66.	ITT	SAFE_T8	Summary of On-Treatment Pneumonia	Include the results of chest X-ray	SAC
Laboratory Parameters					
3.67.	ITT	LB1	Summary of Chemistry Data (On-Treatment)		SAC
3.68.	ITT	LB1	Summary of Change from Baseline in Chemistry Data (On-Treatment)		SAC
3.69.	ITT	SAFE_T9	Summary of Chemistry Data Outside the Normal Range (On-Treatment)		SAC
3.70.	ITT	LB3	Summary of Chemistry Shifts from Baseline Relative to Normal Range (On-Treatment)		SAC
3.71.	ITT	LB1	Summary of Hematology Data (On-Treatment)		SAC
3.72.	ITT	LB1	Summary of Change from Baseline in Hematology Data (On-Treatment)		SAC
3.73.	ITT	SAFE_T9	Summary of Hematology Data Outside the Normal Range (On-Treatment)		SAC
3.74.	ITT	LB3	Summary of Hematology Shifts from Baseline Relative to Normal Range (On-Treatment)		SAC
3.75.	ITT	LB16	Summary of Worst Case Urinalysis Results Post-Baseline Relative to Baseline (On-Treatment)		SAC
Vital Signs					
3.76.	ITT	VS1	Summary of Vital Signs (On-Treatment)	Present BMI as if calculated to 1 decimal place.	SAC
3.77.	ITT	VS1	Summary of Change from Baseline in Vital Signs (On-Treatment)	Present BMI as if calculated to 1 decimal place.	SAC

Safety: Tables					
No.	Population	IDSL ID / Example Shell	Title	Programming Notes	Deliverable [Priority]
3.78.	ITT	EFF_T4	Analysis of Mean Change from Baseline in Systolic Blood Pressure (mmHg) up to Week 24(On-Treatment)		SAC
3.79.	ITT	EFF_T4	Analysis of Mean Change from Baseline in Diastolic Blood Pressure (mmHg) up to Week 24 (On-Treatment)		SAC
3.80.	ITT	EFF_T4	Analysis of Mean Change from Baseline in Pulse Rate (beats/min) up to Week 24 (On-Treatment)		SAC
12-Led ECGs					
3.81.	ITT	EG2	Summary of ECG Values (On-Treatment)		SAC
3.82.	ITT	EG2	Summary of Change from Baseline in ECG Values (On-Treatment)		SAC
3.83.	ITT	SAFE_T10	Summary of ECG Findings (On-Treatment)		SAC
3.84.	ITT	SAFE_T11	Summary of ECG Findings Shifts from Baseline (On-Treatment)		SAC
3.85.	ITT	SAFE_T12	Summary of ECG Abnormalities (On-Treatment)		SAC

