22.	ITT	AE7	Listing of Subject Numbers for Individual Adverse Events		SAC
23.	ITT	AE8	Listing of Non-Fatal Serious Adverse Events		SAC
24.	ITT	AE8	Listing of Fatal Serious Adverse Events		SAC
25.	ITT	AE14	Listing of Reasons for Considering as a Serious Adverse Event		SAC
26.	ITT	AE8	Listing of Serious Adverse Events of Special Interest		SAC

ICH: Listings					
No.	Population	IDSL ID / Example Shell	Title	Programming Notes	Deliverable [Priority]
27.	ITT	AE8	Listing of Adverse Events Leading to Discontinuation of Study Treatment or Early Withdrawal from Study		SAC
28.	ITT	AE8	Listing of Non-Serious Adverse Events Leading to Discontinuation of Study Treatment or Early Withdrawal from Study		SAC
29.	All Subjects Enrolled	AE2	Listing of Adverse Event System Organ Class, Preferred Term and Verbatim Text		SAC
Hepatobiliary (Liver)					
30.	ITT	MH2	Listing of Medical Conditions for Subjects with Liver Stopping Events	IDSL	SAC
31.	ITT	SU2	Listing of Substance Use for Subjects with Liver Stopping Events	IDSL	SAC
All Laboratory					
32.	ITT	LB5	Listing of Chemistry Values for Subjects with at Least One Value Outside the Normal Range	Include data of the form '<X' or '>X'	SAC
33.	ITT	LB5	Listing of Hematology Values for Subjects with at Least One Value Outside the Normal Range	Include data of the form '<X' or '>X'	SAC
34.	ITT	LB5	Listing of Urinalysis Data for Subjects with Any Value of Potential Clinical Importance		SAC
ECG					
35.	ITT	EG3	Listing of All ECG Values for Subjects with an Abnormal ECG Finding	IDSL	SAC
36.	ITT	EG5	Listing of All ECG Findings for Subjects with an Abnormal Finding	IDSL	SAC

ICH: Listings					
No.	Population	IDSL ID / Example Shell	Title	Programming Notes	Deliverable [Priority]
Vital Signs					
37.	ITT	VS4	Listing of Vital Signs		SAC

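### Laboratory results reported as '<x' or '>x' are left out of summary counts even when their side of the normal range is known, and the any-time change rule has no category for Low-to-High or High-to-Low

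*SAP*

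**What the plan says.** Two rules matter, and each has a neighbour that limits it.

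**Censored results.** SAP 11.6.4 (Laboratory Parameters) states: "Non-quantifiable laboratory results will be treated as missing in summary displays". The next sentence adds: "However, the results will be listed as received", with '<x' and '>x' as examples. In SAP 11.10.10, Listing 32, titled "Listing of Chemistry Values for Subjects with at Least One Value Outside the Normal Range", and its hematology counterpart, Listing 33, both carry a programming note to include results of that form.

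**Change from baseline.** SAP 8.5 and 11.6.4 each give two change rules. Under the general rule, the combined 'To Normal or No Change' category takes only participants whose category is unchanged or who return to normal: "Participants who do not change categories or move from out-of-range to normal will be classified as" that category. Under the any-time rule, participants enter 'To Low' or 'To High' only "if they reported a change from a 'Normal' baseline to a value below or above the normal range" (8.5), or "if they reported a change from a 'normal' baseline to a value below or above the normal range" (11.6.4). Its residual category is for those with no reported change to a value outside the range.

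SAP 11.6.4 also defines an any-visit classification of absolute values. It places participants in the low and high categories "if they reported a low or high value at any scheduled or unscheduled on-treatment visit during the study", whatever the baseline.

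**The concern.** A '>x' or '<x' result is not unknown. If x is at or above the upper normal limit, '>x' is High with certainty; if x is at or below the lower limit, '<x' is Low with certainty. Setting such a result to missing discards a category that is known, and it does so because of the value itself. For these results the error runs one way, toward fewer abnormal findings.

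The any-time change rule is a separate matter. It disagrees with the general rule beside it, so a programmer following both would find some participants with no place in the any-time row.

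Hematology and chemistry parameters are listed as secondary safety endpoints (Protocol Section 3, SAP 2.2). Arms are compared mainly through summary tables and figures, so a rule that miscounts participants there is worth correcting even if it seldom applies.

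**Working it through.** The plan states no figure on this point to reproduce. The check applies the wording of SAP 8.5 and 11.6.4 to every combination of baseline category (Low, Normal, High) and on-treatment result (Low, Normal, High, '>x'), which gives 3 × 4 = 12 combinations, 9 of them quantified.

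| Baseline to on-treatment | General change rule | Any-visit absolute row | Any-time change row |
|---|---|---|---|
| Any to Normal; Normal to Low or High (5 of 9) | Classified | Classified | Same as general rule |
| Low to Low; High to High (2 of 9) | To normal or no change | Low; High | Same as general rule |
| Low to High; High to Low (2 of 9) | To high; To low | High; Low | No category fits |
| Any to '>x' (3 of 12) | Missing | Not counted | Not counted as 'to high' |

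**Third row.** The general rule gives 'to high' or 'to low', because the category changed and did not return to normal. The any-time rule cannot, because baseline is not normal. Its residual category does not fit either, because the participant did change to a value outside the range. The two rules conflict in 2 of the 9 quantified combinations and agree in the other 7.

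**Fourth row, where x is at or above the upper normal limit.** Three consequences follow:

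- The result leaves the Low/Normal/High classification at its visit and the any-visit high count. Tables 3.69 (chemistry) and 3.73 (hematology) report values outside the normal range. SAP 11.7.2 also generally drops missing data from percentage denominators.
- SAP 11.6.4 defines maximum post-baseline as the largest on-treatment value. With '>x' missing, a lower value from another visit becomes that participant's maximum in Figures 3.2 to 3.4, 3.7 and 3.8. The notes to SAP Section 8 count figures as well as tables among summaries, so the rule reaches the plots.
- A participant with a normal baseline, one '>x' result and otherwise normal visits has no reported change outside the range once '>x' is missing. The any-time rule then places that participant in 'To Normal or No Change'.

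The mirror case, '<x' with x at or below the lower limit, works the same way for low counts and the minimum plots (Figures 3.5, 3.6, 3.9 and 3.10).

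**Size of one case.** SAP 5.4 gives 766 + 643 + 399 + 631 = 2439 randomized participants. With an equal split, 2439 / 6 = 406.5 per arm, and 1 / 406.5 = 0.25%. If k participants in an arm are affected for one analyte, the count is short by k / 406.5. As assumed values, k = 0 gives 0%, k = 1 gives 0.25% and k = 4 gives 0.98%. The documents give no value for k.

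**The case against.** A reader might infer that the plan hides its most extreme laboratory results. The documents do not support that. The sentence after the rule keeps these results in the listings, Listings 32 and 33 repeat the instruction, and a quantified abnormal value from an abnormal baseline still counts in the any-visit absolute row and still enters the maximum and minimum plots.

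A reader might also infer that every censored result is an abnormal one, so that the summaries as a whole lean toward normal. That does not follow. A '<x' result may lie within the normal range, and '>x' is High only if x reaches the upper limit. The documents give neither assay limits nor normal ranges. Nor does each censored result cost one participant: anyone with another quantified High value stays in the any-visit count, so 0.25% applies only when the censored value is the participant's sole High or Low result for that analyte.

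Clinically important findings also have other routes. Laboratory abnormalities judged clinically significant are reported as adverse events (Protocol 12.4.1), clinically significant values are repeated (Protocol 7.5.7), and liver events have their own criteria and listings.

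All of this stands, and it limits the point to the summary displays. It does not remove it. A listing does not correct a between-arm count, and the absolute row does not give Low-to-High a place in the any-time change row.

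**Conclusion.** The point holds in a limited form. Read literally, the SAP leaves results whose side of the normal range is known out of the categorical laboratory summaries and the maximum and minimum plots. It also counts some participants with a normal baseline as unchanged when they had an abnormal result. Independently, the any-time change rule has no category for Low-to-High or High-to-Low and contradicts the general rule in the same sections.

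The effect cannot be sized from the documents and may be small: 0.25% of an arm for each participant whose only High or Low result for an analyte is censored, assuming equal arms. Low-to-High and High-to-Low changes are expected to be rare. The finding concerns secondary safety displays only; no efficacy result is touched. It rests on reading the missing-data rule literally and on x lying at or beyond the relevant normal limit. It is a minor correction, but one that repairs stated rules that misclassify participants.

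**What to change.** - In SAP 11.6.4, state that for categorical laboratory summaries and shift tables, '<x' and '>x' results are classified as Low or High wherever x settles the category against the normal range. Results that x does not settle stay missing.
- Footnote the number of censored results left out of the continuous summaries and the maximum and minimum plots.
- In both SAP 8.5 and SAP 11.6.4, replace the any-time condition of a normal baseline with a baseline in a different category. Low-to-High then becomes 'To High' and High-to-Low becomes 'To Low', in line with the general rule.

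Substituting x in means is not required. It would conflict with SAP 11.7.2, which imputes no missing numerical data outside the primary-endpoint sensitivity analysis, and it brings its own distortion.

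The cost is a few sentences in two sections, footnotes on the affected laboratory displays, and a small programming step that compares x with the normal range. No endpoint, significance level or efficacy analysis changes.

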## 11.7. Appendix 7: Reporting Standards for Missing Data

### 11.7.1. Premature Withdrawals

Element	Reporting Detail
General	
 
• Withdrawal from Study Prior to Randomization               
 
• Participants who are pre-screening failures, screening failures, run-in failures, or stabilization failures (see Protocol Section 5.5 for the definitions) will be reported to account for the participant disposition.
 
 
 
• Withdrawal from Study Treatment               
 
• Randomized participants who withdraw from double-blind study treatment prematurely (for any reason) should, where possible, continue to be followed-up as per protocol until the end of the study, after returning to the appropriate asthma therapy per investigator's discretion. Post-treatment data will be included in the statistical analyses.
 
 
 
• Withdrawal from Study               
 
• See Appendix 2 for details on data collected at the Early Withdrawal visit.
 
 
 
• Participant study completion (i.e. as specified in the protocol) was defined as 'A participant will be considered to have completed the study upon completion of all assessments and procedures for Visit 8/EOS and including a successful follow-up contact/visit.'
 

### 11.7.2. Handling of Missing Data

Element	Reporting Detail
General	
 
• Missing data occurs when any requested data is not provided, leading to blank fields on the collection instrument:               
 
○ These data will be indicated by the use of a "blank" in participant listing displays unless all data for a specific visit are missing in which case the visit is not displayed in the listing.
 
○ Answers such as "Not applicable" and "Not evaluable" are not considered to be missing data and should be displayed as such.
 
○ No imputation will be made for any missing numerical data, except in the sensitivity analysis of primary endpoints to assess the impact of missing data on study results. Missing data will generally not be considered in the calculation of percentages (i.e., the denominator will not include participants who have missing data at a given time point).
 
 
 

Responder Analysis	
 
• Participants with a missing baseline will have responder status as missing.
 
• Participants with missing data at scheduled clinic visit, regardless of treatment status, will be considered as non-responders.
 
• For ACQ/SGRQ/AQLQ, participants that have withdrawn from study prior to the visit Week 24 will be imputed as non-responders at all visits after early
 

Element	Reporting Detail
	
withdrawal visit where the assessment was expected to be performed, up to Week 24.
 
 
For E-RS and subscales, participants that have withdrawn from study prior Week 24 in question will be imputed as non-responders at time periods post-study withdrawal. This includes time periods up to and including Weeks 21-24.
 

Asthma Control Based on ACQ	
 
Participants with missing data at Week 12 or Week 24 will be classified as not achieving asthma control regardless of reasons in the summaries and analyses.
 
Participants with missing data at baseline will be excluded from the analysis, due to the inclusion of baseline as a covariate.
 

